6.6 REPORTING GUIDELINES

The following guidelines will be followed:

- Page Orientation: Landscape.
- **Post-text tables and listings**: will be generated in .lst and converted to rtf.
- **Post-text figures**: will be generated directly in .rtf.
- **Font**: Courier New font with minimum of 9 points font size.
- Margins: Left: 3.8 cm, Right: 2 cm, Top: 3 cm, Bottom 2 cm on A4 paper.
- Columns headers will be left aligned.
- **Treatment labels** will be the following and displayed in the following order, unless otherwise stated:
 - o GKT831 400mg OD
 - o GKT831 400mg BID
 - o Placebo
 - o **Total**
- Visit labels: the visit labels displayed in Table 1 will be used as required.

Table 1: Visit Labels

Study Stage	CRF Visit	Tables, Figures and Listings Label
Screening	Visit 1 (Screening): Day -28 to -7	SCR
	Visit 2 (Baseline): Day 1	BAS
	Visit 3: Week 2 +/- 3 days	TRT W2
Treatment phase	Visit 4: Week 6 +/- 3 days	TRT W6
Treatment phase	Visit 5: Week 12 +/- 3 days	TRT W12
	Visit 6: Week 18 +/- 3 days	TRT W18
	Visit 7: Week 24 +/- 3 days	TRT W24
Follow-up phase	Visit 8: Week 28 +/- 3 days	FU W28

- Unscheduled visit / repeat assessments: Data obtained at unscheduled or repeat assessments will be taken into account in baseline determination and efficacy summaries based on windowed visits. All other data from unscheduled or repeat assessment will not be included in summaries but only be presented in data listings, unless otherwise specified.
- **N:** The number of subjects in the specified population.
- **Treatment presentation:** The summaries will be presented by allocated or actual treatment group (see more details in Section 7) and overall for disposition, demographics and baseline characteristics, protocol deviations, concomitant medications, study drug exposure and compliance.
- **Continuous data** will be summarized using number of subjects (n), mean, standard deviation (SD), median, minimum value, maximum value and number of missing data (if there are any).
- **Categorical data** will be summarized using n and percentage based on number of nonmissing data.
 - All categories will be presented, even if no subjects are counted in a particular category.
 - In case 1 or more subjects have missing data for the summary, the number of missing data will be presented as a separate category, labelled accordingly as 'Missing', if not otherwise stated.
 - Counts of zero in any category will be presented without percentage.
 - For AEs, medical history, prior and concomitant medications the counts are based on single counts of subjects with multiple events/treatments under same category, while the percentages are calculated using N.
- Precision of summary statistics:
 - Integer Sample size (n, N) and number of missing data (if displayed);
 - One additional decimal place than reported/collected mean, median, other percentile, confidence interval;
 - Two additional decimal places than reported/collected standard deviation;
 - Same number of decimal places as reported/collected minimum, maximum;
 - Percentages one decimal place.
- **Study day** for an assessment will be calculated with reference to the date of first dose as Day 1.

This will be calculated as follows:

(assessment date - date of first dose) + 1 if the assessment date is on or after the date of first dose,

(assessment date - date of first dose) if the assessment date is prior to the date of first dose.

- Data will be presented in listings by allocated treatment group. The order will be subject ID, visit, assessment date/time and assessment type/parameters (in the order collected on e-CRF, unless otherwise specified). For clinical laboratory results, the listings will be presented in the order of allocated treatment group, subject ID, parameter, assessment date/time, visit.
- Dates will be presented in format DD-MMM-YYYY.
- Version 4.03 of the NCI-CTC grading criteria (CTCAE v4) will be used for relevant tables [3].
- Latest version of the Medical Dictionary for Regulatory Activities (MedDRA) will be used for the adverse events coding. The version will be specified in the footnote of the corresponding TFLs.
- Latest version of the WHO-DRUG dictionary will be used for the medications coding. The version will be specified in the footnote of the corresponding TFLs.
- File naming: The name of each TFL output file will start with a t (for a table), f (for a figure) or I (for a listing) to denote the output type and will include an appropriate numbering as well as a reference to the associated domain and analysis set.

7 Analysis Sets

The following populations will be considered in the data analysis:

Randomized population

The Randomized population will include all subjects randomly allocated to a treatment arm. The Randomized population will be analysed by the allocated treatment group.

Intent-To-Treat (ITT) population

The Intent-To-Treat (ITT) population will include all subjects randomly allocated to a treatment arm who have received at least one dose of GKT831 or placebo.

The ITT population will be analyzed by the allocated treatment group and will be the primary population for all analyses of efficacy data.

Per Protocol (PP) population

The Per Protocol (PP) population will include the subjects of the ITT population without a major protocol deviation.

The PP population will be regarded as a secondary population for supportive analyses of efficacy data.

The outputs planned for the PP population will be produced only if there are at least 10% fewer subjects in the PP population compared to the ITT population. That being the case, the PP population will be analyzed by the dispensed study treatment.

Protocol deviations will be defined with the classification of subjects excluded from analysis populations at the end of the study prior to unblinding.

Major protocol deviations will be summarized by the allocated treatment group.

All protocol deviations deemed important will be listed even if not leading to subjects' exclusion from the PP population.

Safety population

The Safety population will include all subjects who have received at least one dose of GKT831 or placebo, irrespective of whether they were randomly allocated to a treatment arm, and had at least one safety assessment.

The Safety population will be analyzed by the dispensed study treatment and will be the primary population for all analyses of safety data.

Pharmacokinetic (PK) population

The Pharmacokinetic (PK) population will include all subjects who have received at least one dose of GKT831, have had at least one valid PK measurement and have had no major protocol deviations relating to PK data.

The PK population will be analyzed by the received treatment group and will be the primary population for the analyses of PK data.

8 Methods of Analyses and Presentations

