# 7.5 Early Termination Visit

If a subject discontinues treatment earlier than Week 24, the following assessments and procedures should be performed and recorded in the Early Termination eCRF. The subject should return to the clinic within 4 weeks after the Early Termination visit for a Final Study visit as detailed in Section 7.4.

- Body weight.
- Urine pregnancy test for female subjects of childbearing potential.

Protocol No.: GSN000300	Compound No.: GKT137831
Protocol Version No.: Final 4.0; Amendment 3	Sponsor: Genkyotex
Protocol Date: 24 July 2018	Author: Cmed Clinical Services

- Blood samples for markers of inflammation and liver injury (hsCRP, fibrinogen, IL-6, CK-18).
- Blood samples for markers of fibrosis (ELF score, collagen fragments).
- Blood samples for optional assessments of immunological markers (IgM, IL-4, IL-12, IL-17A, IFNγ).
- Blood samples for mandatory and optional assessments of bile acid metabolism (serum, C4, total bile acids, FGF-19).
- Blood samples for optional additional biomarkers.
- Blood samples for optional metabolomic studies.
- Transient elastography (FibroScan® or similar technology).
- Safety hematology and biochemistry including blood lipids, triglycerides, liver function tests and INR.
- Thyroid function tests.
- Urinalysis (dipstick).
- PBC-40 QoL questionnaire and pruritus VAS.
- Pulse rate, SBP and DBP.
- 12-lead ECG.
- Symptoms-directed physical examination.
- Concomitant medication recording.
- Recording of AEs.
- Record subject's compliance with treatment regimen until discontinuation of treatment.

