### **10.4.3.8** Other Statistical Analysis Considerations

All safety and efficacy data collected by visit will be summarized regardless of the visit window. For ECG, vital signs, laboratory results and efficacy assessments if there is more than one result

Protocol No.: GSN000300	Compound No.: GKT137831
Protocol Version No.: Final 4.0; Amendment 3	Sponsor: Genkyotex
Protocol Date: 24 July 2018	Author: Cmed Clinical Services

recorded for the same visit the non-missing value closest (if it is a planned, repeat or unscheduled assessment) to the planned day will be used in the summary tables and will be flagged into the corresponding listing. If there is more than one value closest to the planned day, the latest value will be used if the assessment was performed prior to the last dose of IMP.

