## APPENDIX F: CLOSE OBSERVATION PROCEDURES

- 1. Interrupt the investigational agent administration
- 2. Repeat liver biochemistries and additional testing within 24-72 hours
- 3. Monitor patient twice or thrice a week until liver biochemistries (ALT, AST, alkaline phosphatase, total bilirubin, and coagulation profile [INR]) resolve, stabilize or return to within baseline values
- 4. Monitor liver biochemistries once a week if abnormalities stabilize and the patient is asymptomatic
- 5. Obtain a detailed history for symptoms assessment: appearance or worsening of clinical symptoms of hepatitis (fatigue, nausea, vomiting, right upper quadrant pain or tenderness, fever, rash or eosinophilia). If a patient is symptomatic, the drug must be discontinued immediately and a potential DILI evaluation must be performed.
- 6. Obtain a more detailed history of symptoms and prior or concomitant diseases;
- 7. Obtain a history for concomitant medications, acetaminophen, dietary supplements, herbal remedies, other over the counter medications, recreational drug use, and special diets
- 8. If possible quantify the alcohol consumption to assess for alcoholic hepatitis
- 9. Obtain a history of exposure to environmental chemical agents.
- 10. If INR is also elevated, a trial of intravenous vitamin K administration may be considered, especially in cholestatic patients.

Follow-Up Procedures for patient(s) who meet *potential DILI evaluation criteria*:

- 1. Viral hepatitis serology including:
  - a. Hepatitis A IgM antibody;
  - b. Hepatitis B surface antigen and Hepatitis B Core Antibody (IgM);
  - c. Hepatitis C RNA;
  - d. Hepatitis E IgM antibody.
  - e. Cytomegalovirus IgM antibody;
  - f. Epstein-Barr viral capsid antigen IgM antibody (or if unavailable, obtain heterophile antibody or monospot testing); however IgM antibodies must be sent out asap
  - g. Blood sample for pharmacokinetic (PK) analysis, obtained within 12 hours of last dose. Record the date/time of the PK blood sample draw and the date/time of the last dose of study treatment prior to blood sample draw on the CRF. If the date or time of the last dose is unclear, provide the participant's best approximation.
  - h. Serum Creatine phosphokinase (CPK) and lactate dehydrogenase (LDH).
  - i. Fractionate bilirubin, if total bilirubin >2xULN
  - j. Assess for peripheral eosinophilia
  - k. Assess for hypoxic/ischemic hepatopathy; and biliary tract disease

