8.10.2 Clinical Laboratory Evaluations

Laboratory parameters (hematology, biochemistry, TSH levels, urinalysis) results and changes from baseline will be summarized with descriptive statistics by visit for each received treatment group and for all received treatment groups combined.

The changes from baseline will also be displayed by visit for each received treatment group using box plots.

For each laboratory parameter, the incidence of abnormal results (i.e. outside of the normal range) will be summarized by visit for each received treatment group and for all received treatment groups combined. For dipstick parameters with a categorical response, any positive result will be considered abnormal.

For each parameter, the shift from baseline to each planned post-baseline visit in the range of values (low, normal, high and abnormal [low/high]) will be summarized by post-baseline visit with the number and percentages of subjects.

For the calculation of descriptive statistics, all laboratory results will be converted to SI units. Differential counts will be presented both as absolute values and as percentages of white blood cells.

The NCI-CTCAE criteria v4.0 [3] will be used to determine severity.

Template Author: [name] Version 3.0 16AUG2017

For each hematological parameter, the number and percentage of the worst NCI-CTCAE grades will be presented for each received treatment group. The shift from baseline grade to the worst NCI-CTCAE grade will also be presented by received treatment group for each hematological parameter.

For each biochemistry parameter, the same summaries on the worst NCI-CTCAE grades will be produced.

All data will be listed in subject data listings and abnormal results will be flagged.

The laboratory parameters assessments reported as '<LOQ' will be imputed with and displayed as the calculated value equal to LOQ/2 in the listings.

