8.10.4 ECG

ECG parameters include Heart Rate, QRS axis, PR interval, RR interval, QRS duration and QT interval.

In addition, QTcB interval and QTcF interval will be calculated based on the following formulae:

QTcB = QT interval/Square root of RR interval

QTcF = QT interval/Cubed root of RR interval

For all the above ECG parameters, the values as well as the changes from baseline to each planned visit will be summarized with descriptive statistics by visit for each received treatment group and for all received treatment groups combined.

For all the above ECG parameters, the number and percentage of subjects with abnormal results will be presented by visit for each received treatment group and for all received treatment groups combined.

In addition, the shift from baseline to each planned post-baseline visit in the overall ECG interpretation (normal, abnormal not clinically significant and abnormal clinically significant) will be summarized by post-baseline visit for each received treatment group and for all received treatment groups combined.

ECG parameters values will be listed by subject and visit and all results considered abnormal as per criteria defined in Table 3 will be flagged.

QTc Interval	Criteria (msec)	Flag
	≤ 30	Low (L)
Change from Baseline	> 30 to ≤ 60	Mid (M)
	> 60	High (H)
	> 450 to ≤ 480	Low (L)
Actual Value	> 480 to ≤ 500	Mid (M)
	> 500	High (H)

Table 3: Abnormal ECG -Criteria

For QTcB interval and QTcF interval, the categorized values at each visit and the categorized changes from baseline to each post-baseline visit will be summarized by post-baseline visit with the number and percentage of subjects for each received treatment group and for all received treatment groups combined. For both parameters, the categorized worst change from baseline over all planned post-baseline visits will be summarized similarly.

Box plots will be produced for each ECG parameter (Heart Rate, QRS axis, PR interval, RR interval, QRS duration, QT interval, QTcB interval and QTcF interval) showing change from baseline at each visit.

All ECG parameters values will be listed by subject and visit and all results considered abnormal as per criteria defined in Table 3 will be flagged.

9 Interim Analyses

An interim analysis is planned once at least 80-90% of the planned number of subjects to be randomized in the study have completed their Week 6 visit.

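### SAP 6.6 keeps unscheduled and repeat safety results out of the worst-grade and shift tables by default, so off-schedule re-tests after IMP interruption appear only in listings, and Early Termination safety data have no defined visit label

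*SAP*

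**What the plan says.** **General rule.** SAP 6.6 (Reporting Guidelines) says that unscheduled and repeat results "will be taken into account in baseline determination and efficacy summaries based on windowed visits". It then adds: "All other data from unscheduled or repeat assessment will not be included in summaries but only be presented in data listings", with an exception where the SAP specifies something else.

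**Safety sections.** SAP 8.10.2 says that for each hematology parameter "the number and percentage of the worst NCI-CTCAE grades will be presented for each received treatment group". A shift from baseline grade to worst grade follows, and biochemistry is treated the same way. Neither sentence says which post-baseline results are eligible. The normal-range shift table in the same section covers planned visits only. For QTc, SAP 8.10.4 says that "the categorized worst change from baseline over all planned post-baseline visits will be summarized similarly".

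**Protocol rule for the same data.** Protocol 10.4.3.8 covers ECG, vital signs, laboratory results and efficacy. Where a visit has several results, "the non-missing value closest (if it is a planned, repeat or unscheduled assessment) to the planned day will be used in the summary tables". SAP section 10 lists only the two-stage final analysis as a change.

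**Off-schedule testing.** Protocol 6.3.1 to 6.3.3 interrupt IMP at defined liver, anemia and TSH triggers. They call the subject back within 2-3 days (liver, TSH) or 7 days (reticulocytes). For liver events Appendix F adds: "Monitor patient twice or thrice a week until liver biochemistries" resolve, stabilize or return to baseline.

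**Early Termination.** Protocol 7.5 states that "the following assessments and procedures should be performed and recorded in the Early Termination eCRF". The list includes hematology, biochemistry, INR, thyroid tests and a 12-lead ECG. SAP 6.4 presents safety data by eCRF visit without windowing. SAP Table 1 has eight visit labels and none for Early Termination.

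**The concern.** Safety against placebo is the first-listed secondary objective. Protocol 2.3 names liver injury and anemia as risks needing careful monitoring. In 6.3.1 to 6.3.3 the protocol rests its decision on resuming or stopping IMP largely on a re-test. Under SAP 6.6 that re-test is listed but not tabulated.

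The omission is not random. It affects subjects whose IMP was interrupted for a suspected safety problem. If the drug causes such problems, the active arms lose more off-schedule values than placebo, and a worst-value comparison between arms is biased toward no difference. A table titled worst grade would then not show the worst grade observed, and it could disagree with the AE tables for the same subject.

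**Working it through.** The documents give no figure to reproduce. The check is a reading of the rules against each other, followed by a scale calculation.

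**1. Is there an exception for safety?** SAP 6.6 allows one if it is specified. SAP 8.10.2 is silent for worst grade and says planned visits for range shifts. SAP 8.10.4 says planned visits for worst QTc change. No exception is made, so the default applies.

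**2. Are the re-tests really off-schedule?** Post-baseline visits are at Weeks 2, 6, 12, 18, 24 and 28, each within 3 days. The nominal gaps are 14, 28, 42, 42, 42 and 28 days.
- Shortest possible gap from Day 1 to Week 2: 14 − 3 = 11 days.
- Shortest possible gap between later visits: 28 − 3 − 3 = 22 days.

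A re-test 2 to 7 days after a scheduled visit therefore falls before the next visit window opens.

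**3. Which results have another route into a summary?**

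| Result | Route under the SAP |
|---|---|
| Trigger value at a scheduled visit | Stays in all laboratory tables |
| Off-schedule ALT, AST, bilirubin, ALP, GGT | Can enter the windowed efficacy summaries, but SAP 6.4 keeps one value per window, the one nearest the halfway point, so a peak can be missed |
| Off-schedule hemoglobin, reticulocytes, TSH, INR | Not efficacy endpoints; listings only |
| Off-schedule QTc | Listings only; the worst-change table takes planned visits |
| Early Termination laboratory results and ECG | Not excluded; place in by-visit and shift tables undefined |

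SAP 8.10.2 names TSH separately from hematology and biochemistry, so the worst-grade tables may not cover it at all. For TSH the loss is from the abnormality and range-shift tables.

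**4. Would the protocol rule alone solve it?** No. Protocol 10.4.3.8 picks the value nearest the planned day, not the worst. It would let some repeats into by-visit tables, but most re-tests and frequent liver panels would still not be selected.

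**5. Scale.** Change in an arm's incidence for one category = affected subjects / subjects in arm. With 34 per arm (SAP 5.4):
- 1/34 = 2.9 percentage points
- 2/34 = 5.9 percentage points
- 3/34 = 8.8 percentage points

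The documents do not say how many subjects would be affected, so these are unit sizes and not an estimate of bias.

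**The case against.** The case for leaving the plan alone has real substance.

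- **The events are not hidden.** Protocol 9.2.1.3 requires an AE report when an abnormal result leads to IMP being withheld or stopped. AEs carry a CTCAE grade. SAP 8.10.1 tabulates maximal severity, discontinuation and interruption, and treats liver-injury events as of special interest. Off-schedule values are listed with abnormal results flagged. This stands. What the AE tables do not give is the laboratory peak, nadir or shift, and Protocol 9.2.1.3 prefers a diagnosis to the abnormal value itself.
- **The trigger usually survives.** Safety laboratory tests are drawn at every visit, and re-tests follow an abnormality already found. This also stands: the usual loss is later worsening, not the whole event.
- **Worst-grade tables are a SAP addition.** Protocol 10.4.3.4 plans abnormalities and shifts by planned visit. True, but a table presented as worst grade should contain the worst grade.
- **The ECG element is thin.** No interruption rule calls for an unscheduled ECG. It rests on the restriction to planned visits and on Early Termination ECGs.

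A reader might infer more than the text supports:

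- *That off-schedule results are barred from all summaries.* They are not: baseline and the windowed efficacy summaries use them, and those cover the main liver tests.
- *That Early Termination results drop out.* The documents do not say so. Protocol 7.5 defines Early Termination apart from the unscheduled visit in 7.6, SAP 5.2 names it, and SAP 6.4 presents data by the eCRF visit at which they were collected. Nothing removes these results from worst laboratory grade. The missing label leaves their by-visit place undefined, no more.
- *That most liver values are lost.* Two to three panels a week over an assumed four weeks gives 8 to 12 unscheduled panels. The duration is an assumption, Appendix F allows weekly testing once values stabilize and the patient is asymptomatic, and worst-grade tables count subjects, not panels.
- *That an arm's incidence could fall from 5.9% to zero.* This needs two subjects whose abnormality was never seen at a scheduled visit, which is not the usual sequence when scheduled testing raises the alarm.

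**Conclusion.** The point holds as a specific defect in the safety tabulations. Followed as written, the SAP leaves protocol-required re-tests and close-observation panels out of the worst-CTCAE-grade and shift-to-worst-grade tables, and limits worst QTc change to planned visits. Worsening seen only at those assessments is missed, selectively in subjects whose IMP was interrupted. The departure from Protocol 10.4.3.8 is undeclared, and the placement of Early Termination safety data is undefined.

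Each affected subject moves one category's incidence by 2.9 percentage points at 34 per arm. This assumes the subject's worst grade was seen only off-schedule; the number of such subjects is unknown. The direction of bias between arms depends on whether the drug causes more interruptions than placebo. The plan should be corrected, but AE reporting limits the harm.

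**What to change.** 1. In SAP 6.6, 8.10.2 and 8.10.4, state that worst CTCAE grade, shift to worst grade and worst QTc change use all post-baseline results (planned, repeat, unscheduled and Early Termination) up to 28 days after last dose. The cut-off matches the protocol's AE recording period.
2. Add an Early Termination label to SAP Table 1 and to the by-visit safety tables.
3. For by-visit values, apply Protocol 10.4.3.8, or declare and justify the departure in SAP section 10. This step alone is not enough, because the value nearest the planned day need not be the worst.

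The cost is SAP wording and a little more programming on data already collected. By-visit tables gain a row, and abnormality rates may rise slightly in all arms.
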